8.2 Secondary Outcome and Analyses

A variety of secondary analyses are planned, some of which will include the following :

- Subgroup analyses may be conducted comparing the effects of low-dose ATG versus control on the risk of diabetes within subsets of the study cohort. Subgroups of the population may be classified by age, gender, race/ethnicity, specific antibody status at baseline, and HLA status (e.g. presence or absence of HLA DR3/DQ2 and/or HLA DR4/DQ8). Differences in the treatment effect between subgroups will be tested using a covariate by treatment group interaction term in the Cox regression model.
- The heterogeneity of treatment effect across categorical factors will be assessed through a covariate by treatment group interaction in a Cox hazards regression model. These factors include gender, race/ethnicity, specific antibody status at baseline and HLA status (i.e. presence or absence of HLA DR3/DQ2 and/or HLA DR4/DQ8).
- Similarly, subset analyses will be conducted using the values of quantitative baseline factors (dichotomized at the median) Including weight, BMI-Z, CBC and the immunologic and metabolic factors described in Section 5 that include autoantibody titers, basal c-peptide, OGTT stimulated c-peptide (peak and AUC-mean).
- Additional covariates may be defined during the conduct of the study. The reporting

of the analyses will distinguish between factors specified prior to primary analysis and those identified post-hoc during analysis.

- Longitudinal analyses will assess the effects of low-dose ATG versus control treatment on immunologic and metabolic markers over time up and following progression to stage 3 T1D. Differences between groups in the mean levels of quantitative factors over time will be assessed using a normal errors linear model for repeated measures. Differences between groups in the prevalence of qualitative factors over time will be assessed using generalized estimating equations for categorical measures. Generalized estimating equations may also be employed for the analysis of quantitative factors when the normal errors assumptions are violated.
- The association of demographic, genetic, immunologic, metabolic, and lifestyle factors, among others, both at baseline and over time, with the risk of diabetes onset will be assessed in Cox regression models over time. The effects of changes in longitudinal factors on diabetes risk will be assessed using time-dependent covariates for these factors. Analyses will be conducted separately within the treatment and control groups, and differences between groups in covariate effects (group by covariate interactions) will be assessed. Longitudinal analyses of C-peptide AUC means 3, 6, 9, 12, 18, 24, 30, 36, 42, 48, 54 and 60 months using a mixed effects model with a random intercept and slope by participant, adjusted for the baseline level of C-peptide, gender and baseline age. The mean intercept and slope will be compared between treatment groups.
- Toxicity and tolerability will also be assessed in all participants who have received at least one dose as part of this trial. Toxicity is defined as an adverse event that is classified as either possibly, probably, or definitely related to study treatment. The maximum grade for each type of toxicity will be recorded for each participant, and frequency tables will be reviewed to determine toxicity patterns. In addition, we will review all adverse event data that is graded as 3, 4, or 5 and classified as either “unrelated” or “unlikely to be related” to study treatment in the event of an actual relationship developing.
- The incidence of severe (grade 3+) adverse events or toxicities will be described for each treatment arm but will also be compared between the arms. Fisher’s exact tests will be used to quantitatively compare the incidence of severe as well as specific toxicities of interest between the treatment arms, and we will graphically assess differences in maximum grades observed for toxicities between the arms. Fisher’s exact test on adverse events will be used for descriptive purposes only; p-values provided will be nominal p-values (there is no correction for multiplicity planned, so no inferential conclusion can be drawn from there). These analyses will be useful in identifying potentially toxicity patterns of interest and in planning future trials. We will also assess tolerability of low-dose ATG through assessing the proportion of people who discontinue treatment due to adverse reactions or even those who refuse further treatment for lesser toxicities that inhibit their willingness to continue participation on the trial. These tolerability measures will be assessed within each of the treatment arms and we will explore differences in these measures

between the arms. All participants who have received at least one dose of any of the therapeutic agents in a treatment arm will be evaluable for toxicity and tolerability.

Additional secondary objectives to determine the effect low-dose ATG on metabolic and immunologic measures such as but not limited to:

- HbA1c over time by treatment group using ANCOVA.
- Index 60
- AUC Glucose post OGTT
- CGM variables and metrics
- Descriptive Assessment of Safety and Tolerability of Adverse events to include but not limited to:
 - Number and severity.
 - The rates of severe adverse events will be computed (total number of events divided by total participant years of follow-up)
- CD4:CD8 panel

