General disorders and administration site conditions	Chills	1	1	0	0
	Fatigue	1	1	0	0
	Fever	2	2	0	0
	Flu like symptoms	2	3	0	0
	General disorders and administration site conditions - Other, specify	1	1	1	1
	Pain	2	2	0	0
Immune system disorders	Cytokine release syndrome	11	14	0	0
	Serum sickness	13	13	0	0
Infections and infestations	Otitis media	0	0	1	1
	Pharyngitis	1	1	0	0

TABLE 4: Non-Serious Adverse Events Reported in TN19 Study for Participants Ages 12-17					
		Attribution #			
Systems Affected (CTC 4.0)		Non-serious - related		Non-serious - unrelated	
Category	AE term	Number of Participants	Number of Adverse Events	Number of Participants	Number of Adverse Events
	Rash pustular	0	0	1	1
	Skin infection	0	0	1	1
	Upper respiratory infection	0	0	2	2
	Urinary tract infection	0	0	1	1
Injury, poisoning, procedural complications	Fracture	0	0	1	1
Investigations	CD4 lymphocytes decreased	8	9	1	1
	Investigations - Other, specify	1	1	0	0
	Lymphocyte count decreased	11	13	0	0
	Neutrophil count decreased	2	3	1	1
	White blood cell decreased	4	5	0	0
Metabolism and nutrition disorders	Hypoglycemia	0	0	1	2
Musculoskeletal / connective tissue disorders	Pain in extremity	1	1	0	0
Nervous system disorders	Headache	3	9	0	0
	Nervous system disorders - Other, specify	0	0	1	1
Skin and subcutaneous tissue disorders	Rash maculo-papular	1	1	0	0
	Skin and subcutaneous tissue disorders - Other, specify	1	1	3	7
	Urticaria	0	0	2	2
Vascular disorders	Hypotension	1	1	0	0
	Phlebitis	1	1	0	0

In summary, clinical trial data from two independent studies in Stage 3 T1D have demonstrated efficacy in preserving C-peptide and lowering A1c in persons and suggest equal if not greater effects on metabolic responses in children compared to adults ^{6,61}.

In the 2023 published case study, similar side effects were experienced in 6 pediatric participants who presented as at-risk for developing stage 3 T1D. CRS was reported in half of these participants and all had experienced serium sickness. No additional drug-related adverse events beyond CRS and SS were reported. 3 participants remained diabetes-free at 18 months, 3 years and 4 years respectively after treatment with ATG².

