7.4 Adverse Events of Special Interest

An adverse event of special interest (AESI) can be serious or non-serious but is one of concern specific to the sponsor’s product. Adverse events categorized as such require ongoing monitoring and rapid communication by the investigator to the sponsor. AESIs grade 1 or higher will be reported electronically to the TNCC. The DSMB and the FDA will be notified of Grade 3 or greater or hospitalization events in relation to Serum Sickness. AESI include the following conditions/symptoms:

- Anaphylaxis
- Cytokine Release Syndrome
- Hematologic Effects (i.e. lymphopenia, Neutropenia, thrombocytopenia)
- Serum Sickness
- Infections
-

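### Section 8.2 bases the between-arm toxicity tests on investigator attribution, so low-grade events of special interest rated unrelated, including infections, have no stated comparison between arms

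*Combined protocol and SAP*

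**What the plan says.** Section 8.2 sets the term first: "Toxicity is defined as an adverse event that is classified as either possibly, probably, or definitely related to study treatment". Sections 7.6 and 7.7 give the rating to the site investigators, on a five-level scale.

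Section 8.2 then describes these safety analyses:

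- For severe events: "The incidence of severe (grade 3+) adverse events or toxicities will be described for each treatment arm", and the same sentence adds a comparison between arms.
- Fisher's "exact tests will be used to quantitatively compare the incidence of severe as well as specific toxicities of interest between the treatment arms". The toxicities of interest are not listed.
- Graphs of the maximum grade by arm, again for toxicities.
- For events rated unrelated or unlikely: "we will review all adverse event data that is graded as 3, 4, or 5 and classified as either" of those two ratings. Grades 1 and 2 are not mentioned.
- A descriptive summary of adverse event number and severity, and a severe-event rate per participant-year. Neither carries a relatedness filter.

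On the status of the p-values, Fisher's "exact test on adverse events will be used for descriptive purposes only".

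Section 7.4 opens its list with "AESI include the following conditions/symptoms", and infections are on that list. AESIs are reported from grade 1, and other adverse events from grade 2 (7.7).

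**The concern.** In a randomised, placebo-controlled trial the control arm shows how often an event occurs without the drug. Filtering by an investigator's opinion of cause adds no protection against confounding. It discards events and brings in a judgement that may differ between arms.

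Infection is where this matters most. Section 6.2.1 describes a raised relative risk of opportunistic infection while lymphocytes recover, and section 2.3.1 says CD4 counts can stay low for 12 months. An ordinary childhood infection is easily put down to background, yet an excess of ordinary infections is what the between-arm table should be able to show.

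The rating may also not be independent of the arm. Section 6.2.1 expects serum sickness in about three quarters of ATG participants. Blood counts and CD4/CD8 panels are run locally (Appendix 1). If such signs influence the rating, a related-only comparison could hide a real difference or suggest one that does not exist.

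**Working it through.** **1. Which events have a stated between-arm comparison in 8.2**

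| Event | Stated comparison |
|---|---|
| Grade 3+, rated related | Yes |
| Grade 3+, rated unrelated or unlikely | Apparently yes, if the joint phrase in "The incidence of severe (grade 3+) adverse events or toxicities will be described for each treatment arm" covers all adverse events; also reviewed |
| Grade 1–2, rated related | Yes: Fisher test if of interest, and maximum-grade graphs |
| Grade 1–2, rated unrelated or unlikely | None stated; only the overall number and severity summary |

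The last row is the gap. The second row is an ambiguity: the sentence joins adverse events and toxicities, the next sentence tests toxicities, and a later one calls it a test on adverse events. Two analysts could build different tables.

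**2. How attribution treated infections in TN19 (ATG-only participants, section 2.3.2)**

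The protocol's own figure first: Table 4 (children) sums to 89 related + 26 unrelated = 115, and 89/115 = 77.4%, as stated. Table 2 (adults) sums to 38 + 13 = 51, and 38/51 = 74.5%. The text says 75.5%, a minor separate mismatch.

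Infection rows, in events:

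- Children: related 1 (pharyngitis). Unrelated 6 (otitis media 1, pustular rash 1, skin infection 1, upper respiratory infection 2, and 1 listed as "Urinary tract infection").
- Adults: related 3 (sinusitis 1, upper respiratory infection 2). Unrelated 1 (upper respiratory infection).
- Pooled: 7/11 = 64% unrelated, exact 95% CI 31% to 89%.

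Against other events, in children 1/7 = 14% of infections were rated related, compared with (89 − 1)/(115 − 7) = 88/108 = 81% of the rest. In adults it was 3/4 = 75%, compared with (38 − 3)/(51 − 4) = 35/47 = 74%. So the filter falls harder on infections in children, with no such pattern in adults.

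**3. How informative serum sickness is about the arm**

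TN19 had 29 ATG-only participants (2.3), 10 of them adults (2.3.2), hence 19 children. Serum sickness: adults 7/10; children 13 non-serious plus 1 serious, so 13 or 14 of 19. In total that is 20–21 of 29, or 69–72%, consistent with three quarters.

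With 2:1 allocation, rate s = 0.75 on ATG and an assumed rate q = 0 to 0.10 on placebo (no placebo rate is given):

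- P(ATG | serum sickness) = 2s/(2s + q) = 1.5/1.5 to 1.5/1.6 = 100% to 94%.
- P(ATG | none) = 2(1 − s)/[2(1 − s) + 1 − q] = 0.5/1.5 to 0.5/1.4 = 33% to 36%, against 67% beforehand.

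**4. What the filter could do to a test (assumed rates)**

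The documents give no infection rates. The table shows the exact power of a two-sided Fisher test at 0.05, 68 v 33, where a proportion of participants have any infection. The related-only column keeps 4/11 of that proportion in both arms. This applies an event share to participants and assumes every infection is below grade 3.

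| ATG v placebo (assumed) | All events | Related only |
|---|---|---|
| 40% v 20% | 47.8% | 10.5% |
| 50% v 20% | 81.9% | 22.5% |
| 30% v 10% | 58.6% | 10.7% |

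In the other direction, suppose there is no true difference but 4/11 of infections are rated related on ATG and 1/11 on placebo. That split is an assumption with no source in the documents. At 30%, 40% and 50% in both arms, the related-only test then rejects 14%, 27% and 40% of the time; the all-event test rejects 3.8%, 3.5% and 3.4%.

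**The case against.** The strongest reply is that the plan has several all-cause routes and that little depends on this table. Most of that stands. Grade 3+ events appear to be compared by arm regardless of cause, all-cause number and severity are summarised, and the DSMB reviews adverse events by treatment group every three to six months (7.7). Stopping rule 8 in 5.8 counts clinical mononucleosis in EBV-seropositive participants from 5 days to 6 months after dosing without an attribution test. The p-values are nominal, and no decision rule depends on them. None of this supplies a stated between-arm comparison for grade 1–2 AESIs rated unrelated, and nominal status does not repair a numerator that depends on opinion.

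A reader might infer three stronger things, which the documents do not support:

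- *That only drug-related events are compared.* The grade 3+ sentence and the all-cause summaries contradict this.
- *That most infections would be dropped.* The TN19 counts are 11 events, ungraded, possibly clustered within participants, and reversed in adults. Any of grade 3+ would fall in the severe-event comparison as it is most naturally read. No TN19 placebo infections are shown.
- *That serum sickness in effect unmasks the raters.* This is plausible for participants who have it, but its absence is only weakly informative and no placebo rate is given. Personnel other than the pharmacist are masked (4.3), and the medical monitor reviews reports masked (10.3.5). In TN19, where about 70% had serum sickness, 6 of 7 infections in children were still rated unrelated, which gives no sign that perceived ATG assignment pushes ratings towards related.

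**Conclusion.** The point holds in limited form. Section 8.2 ties the Fisher tests on selected toxicities and the maximum-grade graphs to investigator attribution, so grade 1–2 AESIs rated unrelated have no stated comparison between arms, and the treatment of unrelated grade 3+ events rests on an ambiguous phrase. An all-cause comparison is the better method here and needs no new data.

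The effect on this trial cannot be sized from the documents. The TN19 share (7 of 11; 6 of 7 in children, 1 of 4 in adults) illustrates how attribution can treat infections and is not an estimate of what would be lost. The power and false-positive figures depend on assumed infection rates and attribution shares. Influence of serum sickness on the rating is a reasonable concern, not a demonstrated one. Because the analysis is descriptive and other all-cause summaries exist, this is a cheap improvement, not a flaw that endangers the trial's conclusions.

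**What to change.** In 8.2, state that the between-arm tables, Fisher tests and maximum-grade graphs use all treatment-emergent adverse events regardless of causality rating, for each AESI category in 7.4 and for all grade 3+ events. Define treatment-emergent there. Replace the joint phrase on adverse events or toxicities with adverse events alone. Keep the related-only toxicity table by arm as a descriptive supplement, and keep the p-values nominal.

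The cost is wording only. AESIs from grade 1 and other adverse events from grade 2 are already reported whatever their attribution (7.1, 7.4, 7.7). The downside is that some background events will enter both arms' tables, which randomisation accounts for and the supplement helps the reader to see.

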3 STUDY DESIGN

3.1 Overview

This study is a 2-arm, multi-center, double blinded, 2:1 randomized, placebo-controlled clinical trial. The trial will investigate whether intervention with ATG will delay or prevent progression to Stage 3 T1D in individuals identified with a 2-year 50% risk for progression to Stage 3 T1D. A total of 101 people with 2-year 50% risk of progression to T1D will be enrolled. The treatment phase will consist of 2 infusions over 2-3 days. Participants will be followed up for at least 24 months from randomization. Participants who progress to stage 3 T1D will be followed to explore the treatment effect on C-peptide retention for at least one year.

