4.7 Infectious Disease Screening

All participants will be strongly encouraged to be fully vaccinated for COVID-19 with an approved COVID-19 vaccine at least 2 weeks prior to enrollment. All participants will be asked to follow guidelines for social distancing and will be asked to wear a mask when outside of their home. Participants will be assessed for COVID-19 symptoms and close exposure to an individual diagnosed with COVID-19 at each study visit and before beginning study treatment with ATG/Placebo. Participants are required to be free of COVID-19 symptoms for 14 days prior to the screening visit and before the first infusion is administered. COVID-19 testing may be performed as required per local public health or institutional guidelines. A COVID-19 test is required to be done within 7 days of the enrollment visit (infusion 1). Point of care antigen test kits are acceptable.

Beyond that, no specific infectious diseases prophylaxis is warranted in this study. This decision is based on the limited duration and dose of exposure to ATG. In lieu of active serologic or virologic monitoring strategies, all participants will be counseled on an ongoing basis on the importance of notifying their research centers about the presence of signs or symptoms suggestive of infection especially over the 3 months after the infusion. They will also be counseled on the importance of notifying the research center about potential exposures to varicella, influenza, COVID-19 or other

infectious illnesses. In addition, during the first 2 weeks post ATG infusion, all research participants will be contacted every other day and queried about the presence of signs or symptoms (e.g. fever, rhinorrhea, cough, sore throat, mouth sores, myalgia, arthralgia, etc.) that might represent markers of active infection or serum sickness. From 2 weeks post infusion to 3 months after the infusion, participants will be contacted weekly to monitor for symptoms of infection and/or illness. Specific algorithm(s) for the evaluation and management of those study participants identified as having signs and/or symptoms concerning for infection are provided in the manual of operations for this study and are directed based on the participant's specific symptomatology. This will provide general and, in some cases, specific recommendations for the assessment of study participants.

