6.2 Potential Risks

6.2.1 ATG

ATG has been widely used in transplantation and autoimmune disorders⁴⁷. In the ITN START study, participants received ATG at a total dose of 6.5 mg/kg, a dose which has been effective and well tolerated in bone marrow and solid organ transplantation, and well below the dose of 20 mg/kg that has been used for some transplantation protocols. For this study, the doses will be administered as 0.5 mg/kg during the first infusion and 2 mg/kg during the second infusion to reduce adverse reactions. ATG will be given over at least 6 hours for both infusions. Participants will receive pre-medication with acetaminophen and diphenhydramine (or equivalent) and participants randomized to active therapy will receive methylprednisolone prior to the infusion that contains ATG. This is to minimize side effects from possible cytokine release syndrome (CRS). Participants will be closely observed in the hospital/outpatient setting during the treatment period and will be contacted between treatments for assessment of adverse events and management should they occur. Symptoms of CRS may include fever, chills, rigors, headache, tremor, nausea, vomiting, diarrhea, abdominal pain, muscle and joint pain, and malaise. Anaphylactic reactions have been rarely reported with ATG. Delayed reactions such as serum sickness occur in approximately $\frac{3}{4}$ of actively treated participants between 9-14 days post-infusion. Thrombophlebitis may also develop following infusion with ATG.

ATG contains a variety of antibodies that may cross-react with cell-surface markers. ATG causes lymphocyte depletion with marked depletion of lymphocytes occurring acutely. The circulating number of T cells increases with cessation of therapy, usually reaching pre-treatment levels of CD8+ T cells by 2 months. Participants are at low absolute but relatively increased risk for opportunistic infection during this window of recovery and will receive close surveillance for primary viral infections, viral reactivations, and bacterial infections^{71,72}.

ATG may also lead to leukopenia and thrombocytopenia. Effects are dose-dependent and are mainly encountered with over dosage. In up to 3% severe thrombocytopenia may occur but this is invariably seen in doses 4-5 times that which we are proposing. Thrombocytopenia in these participants often occurred in a postoperative transplant setting and with other immunosuppressants.

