- ATG Drug Induced Antibodies (DIA): Samples will be drawn on 12 participants in each of the following age groups: <18 years and ≥ 18 years at randomization. Pre-infusion sample will be drawn on Day 0. Samples will also be drawn on Days 4 and 7, Week 2, and Month 3.
- May include samples for RNA, plasma, serum, DNA, measures of B and T cell number and function to understand the effect of therapy on the immune system and infectious disease. The following HLA typing will also be performed: Class I (HLA-A, B, C) and Class II (DRB, DBA, DQB). The schedule for these assessments may vary as appropriate. At no time will the blood draw volume exceed what is allowable according to the participant's age and body weight (for participants <18 years, 5 mL/kg per visit, 9.5 mL/kg in an 8-week period).
- Contact with participant every other day will occur once the study treatment is complete until the 2-week visits. Following the 2-week visit weekly contact with participant will occur until the 3-month visit. Contact thereafter will occur every 3 months, in-between in person study visits to assess for symptoms of diabetes and changes in health. Participants who report signs/symptoms consistent with Stage 3 T1D will be asked to complete a PRN OGTT study visit. At any time point in between study visits, participants experiencing symptoms of diabetes are to contact their clinical trial contact(s). Covid-19 assessments may be completed PRN through the end of the study based on exposure and symptoms.
- Participants are required to receive killed influenza vaccination at least 2 weeks prior to randomization when vaccine for the current or upcoming flu season is available.
- Frequency of CGM blinded, 7-10 day wear will occur at the screening visit, 3 month visit and then semi-annually per schedule of visits.
- Fecal sample: Willing participants will collect fecal samples within +/-3 days of the indicated visit at home and either bring to the research visit or ship samples back to the site. Participants who agree to collect samples should be encouraged to provide samples at all 3 timepoints.
- The bi-annual schedule will continue until the primary endpoint of the study occurs. After the primary endpoint is met, all participants will be followed for an additional year. Participants who develop Stage 3 T1D at any point during the year post-primary endpoint, will be followed for 1 year following their diagnosis.

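### The pooled severe adverse event rate per participant-year falls as follow-up lengthens, because ATG is given once and its known reactions come early; fixed windows should lead

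*Combined protocol and SAP*

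**What the plan says.** Section 8.2 lists the rate under this item: "Descriptive Assessment of Safety and Tolerability of Adverse events to include but not limited to". The definition reads: "The rates of severe adverse events will be computed (total number of events divided by total participant years of follow-up". Nothing in Section 8 divides safety data by time since infusion.

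The same section also plans summaries per participant. One begins "The incidence of severe (grade 3+) adverse events or toxicities will be described for each treatment arm" and goes on to a comparison between arms by Fisher's exact test, with p-values declared nominal. The section adds Fisher tests for specific toxicities and a display of maximum grades by arm. Everyone who received at least one dose is evaluable.

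Three features of the design bear on the rate:

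- **Exposure is brief.** Section 3.1: "The treatment phase will consist of 2 infusions over 2-3 days".
- **Expected reactions are early.** Section 4.5.1 places cytokine release syndrome with the infusion. Section 4.5.3 places serum sickness 7 to 15 days after the first dose. Section 6.2.1 says "Delayed reactions such as serum sickness occur in approximately" three quarters of those given ATG, at 9 to 14 days, and describes lymphocyte depletion as acute.
- **Follow-up is long.** It lasts at least 24 months and at least 12 months beyond the primary endpoint (Section 3.6). The Appendix 1 schedule runs to month 60.

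The protocol already treats the first three months as a separate period of contact (Section 4.7): "during the first 2 weeks post ATG infusion, all research participants will be contacted every other day", and then "From 2 weeks post infusion to 3 months after the infusion, participants will be contacted weekly".

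**The concern.** A single rate of events per participant-year is a fair summary when the event rate is roughly constant over the time counted. Here the drug-related part of the risk is expected within weeks of one course of treatment, and most of the denominator is accumulated years later. The ATG figure then reflects how long participants happen to have been followed as well as how often the drug caused a severe event.

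The same early harm would give a lower rate in the final report than in a mid-trial one, and a lower rate in this trial than in a shorter one. The figure would also say little about the risk that a participant or parent faces in the weeks after infusion. Safety matters a good deal in a trial that enrols children from age 6.

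**Working it through.** The documents state no severe adverse event rate, so there is no figure of the plan's own to reproduce. The check applies the plan's formula.

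**Formula.** Suppose N ATG participants have p early severe events each, plus background events at constant rate b. Total events are Np + bNT and total participant-years are NT, where T is mean follow-up. The pooled ATG rate is (Np + bNT)/NT = b + p/T. The placebo rate is b. The difference between arms, p/T, shrinks with T whatever b is.

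**Inputs.** The documents give no general grade 3+ rate for this dose, so p and b are assumed over ranges: p = 0.10, 0.30 and 0.75, and b = 0, 0.05 and 0.10 per year. The top value of p would mean that all expected serum sickness is severe.

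T = 2 years is the minimum follow-up. T = 4.4 years is the mean in 20,000 simulated trials on the Section 8.4 assumptions:

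- 50% control risk at 2 years, hazard ratio 0.4, 4-year uniform accrual and 10% two-year dropout
- follow-up to one year after the 44th event or after the two-year minimum for the last entrant, whichever is later

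That gives about 301 ATG participant-years over 68 participants (301/68 = 4.4). If the 44th event alone set the end, the mean would be about 3.9 years.

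**Pooled rate per 100 participant-years**

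| p | b | ATG, T = 2 | ATG, T = 4.4 | Placebo |
|---|---|---|---|---|
| 0.10 | 0.10 | 10 + 10/2 = 15.0 | 10 + 10/4.4 = 12.3 | 10 |
| 0.30 | 0.10 | 10 + 30/2 = 25.0 | 10 + 30/4.4 = 16.8 | 10 |
| 0.75 | 0.10 | 10 + 75/2 = 47.5 | 10 + 75/4.4 = 27.0 | 10 |
| 0.30 | 0.05 | 5 + 30/2 = 20.0 | 5 + 30/4.4 = 11.8 | 5 |
| 0.30 | 0 | 30/2 = 15.0 | 30/4.4 = 6.8 | 0 |

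In the second row the ATG-to-placebo ratio goes from 2.5 to 1.7 with the same early harm. At T = 3.9 the ATG rate is 10 + 30/3.9 = 17.7, so the choice of end date matters little. The first three months supply 68 × 0.25 = 17 of the 301 ATG participant-years, about 5.6%.

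**The planned incidence per participant.** The proportion with at least one severe event by time T is 1 − (1 − p)exp(−bT) on ATG and 1 − exp(−bT) on placebo. With p = 0.30 and b = 0.10:

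- 3 months: 1 − 0.7 × 0.975 = 32% against 2%
- 2 years: 1 − 0.7 × 0.819 = 43% against 18%
- 5 years: 1 − 0.7 × 0.607 = 58% against 39%

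The ratio falls from 2.4 at 2 years to 1.5 at 5 years. Without a window, this summary also mixes early reactions with years of background events.

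**With fixed windows.** For the same p and b, the rate from infusion to month 3 is (0.30 + 0.10 × 0.25)/0.25 = 1.30 per year, or 130 per 100 participant-years, against 10 on placebo. After month 3 it is 10 in both arms. Neither figure depends on total follow-up.

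**The case against.** The strongest reply is that the plan does not rely on this rate. It is one descriptive line. The plan also has grade 3+ incidence per participant, Fisher tests for specific toxicities and maximum-grade summaries, none of which uses participant-time. The stopping rules in Section 5.8 work on events and counts, and no section ties a decision to the pooled rate. For cytokine release syndrome and serum sickness taken singly, incidence per participant is in effect already an acute measure. All of this stands and keeps the point small. It does not rescue the pooled rate, and the incidence of any grade 3+ event remains unwindowed.

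A reader might infer three stronger points that the documents do not support:

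- **That thinner contact later pulls the rate down.** Appendix 1 says: "Contact thereafter will occur every 3 months, in-between in person study visits to assess for symptoms of diabetes and changes in health". That lowers a severe-event rate only if severe events go unreported, and nothing in the documents shows this. Section 7.7 describes grade 3 events in terms of hospitalization or invasive intervention, and both appendices assess adverse events at every follow-up visit. Under-capture would also affect both arms. If half of the events after month 3 were missed (p = 0.30, b = 0.10), background events over 2 years would be 0.10 × 0.25 + 0.5 × 0.10 × 1.75 = 0.1125 per participant. The rates would be (0.30 + 0.1125)/2 = 20.6 and 0.1125/2 = 5.6 per 100, and the ratio would rise from 2.5 to 3.7.
- **That placebo safety is under-observed after Stage 3.** More placebo than ATG time would follow diagnosis only if ATG works as assumed. Appendix 2 has no interim-contact row, but Section 4.8 promises continued regular contact by the research team.
- **That the rate falls about 18-fold.** That is 4.4/0.25 with no background events, starting from a rate at 3 months of follow-up that no section plans to report. With b = 0.10 the same comparison gives about 4-fold at p = 0.10 (50 to 12.3), 8-fold at p = 0.30 (130 to 16.8) and 11-fold at p = 0.75 (310 to 27.0).

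**Conclusion.** The point holds in a limited form. As defined, the pooled rate is b + p/T, so early ATG harm is diluted as follow-up grows. In the central example it goes from 25 to about 17 per 100 participant-years between 2 and 4.4 years, against 10 on placebo. Over the assumed values of p at b = 0.10, the fall runs from 15.0 to 12.3 up to 47.5 to 27.0.

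The direction rests on the protocol's own account of when reactions occur. The size rests on assumed p and b and on a simulated mean follow-up. The upper value of p should not be read as expected. The three-quarters figure in Section 6.2.1 gives no grade. All six children in the case series had grade 3 serum sickness (Section 2.3), but the TN19 tables list 7 + 13 = 20 related non-serious reports and 1 related serious report, without grades.

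The documents do not support saying that the plan would hide severe ATG toxicity. This is a cheap improvement to reporting, not a defect in the safety monitoring.

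**What to change.** Amend Section 8.2 so that grade 3+ adverse events are reported by arm, among all who received at least one dose, in windows fixed from the first infusion:

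- infusion to month 3, which matches the intensive-contact period in Section 4.7
- after month 3, optionally split at month 12, because Section 2.3.1 says that CD4+ counts can stay reduced for 12 months

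Make the infusion-to-month-3 proportion per participant the lead safety summary, and apply the Fisher comparison already planned to it, still as descriptive. Keep the pooled participant-year rate only beside these figures, with mean follow-up by arm.

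Do not cut the periods at Stage 3 diagnosis for comparisons between arms. Diagnosis is the primary outcome and may be affected by treatment, so the groups after it are no longer the randomised ones.

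The cost is SAP wording and one table built from infusion and event dates, with no added visits. Counts per window will be smaller. With 68 and 33 participants, 20 against 0 in the first window gives a nominal Fisher p of 0.0001, and 7 against 0 gives 0.09. The table should therefore be read mainly through the proportions.
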